1.1.1 Profile of MGL-3196, Preclinical and Clinical Data

MGL-3196 is a liver-directed, orally active, partial agonist for the thyroid hormone receptor (THR), with approximately 28-fold selectivity for the beta receptor compared to the active thyroid hormone, triiodothyronine (T3). MGL-3196 was selected for clinical development based on its enhanced THR- β selectivity in functional THR assays and its greatly improved safety in preclinical animal models relative to other THR analogues and T3.¹⁹ Unlike previous clinical analogues which are, in fact, potent at the alpha receptor like thyroid hormone, MGL-3196 is highly THR- β selective in a functional coactivator recruitment assay and has virtually no THR- α activity.¹⁹ Liver uptake is mediated by hepatic transporters and, systemic exposure is limited by high protein binding and low tissue penetration outside the liver. In preclinical animal studies, MGL-3196 showed rapid and robust lowering of non-HDL cholesterol, triglycerides, and liver triglycerides, differentiating MGL-3196 from statins and other lipid-lowering agents. In a rabbit model, MGL-3196 showed excellent lipid lowering, including cholesterol and triglycerides when administered alone, and an additive effect of MGL-3196 was observed when administered in combination with atorvastatin.

Preclinical studies, including acute, subchronic, reproductive and chronic animal toxicology studies support the Phase 2 studies. The toxicities observed in both toxicological animal species, rats and dogs, were generally reversible, reflective of pharmacology on the drug target, and were not serious or life-threatening. Between the range of possible clinical doses (80-120 mg per day) a dose of 80 mg is 11,13 fold, and 120 mg is 5,6 fold below the NOAEL in the rat and dog, respectively (Investigator Brochure) and 29-49 fold below the maximum dose that was generally well tolerated, and, while not the NOAEL, in rat was due to monitorable HPT suppression, and in dog, generally monitorable biliary hyperplasia which was associated with elevated ALP. In rats or dogs, no histologic effects on cartilage (or bone) were observed at any dose (NOEL in dogs 62 fold relative to expected clinical exposure at 80 mg), clearly differentiating MGL-3196 from eprotirome.

To date, a total of 129 healthy volunteers have received oral doses of MGL-3196 ranging from single doses of 0.25 to 200 mg, to multiple once-daily oral doses from 5 to 200 mg for up to 14 days. The single and multiple ascending dose studies were placebo controlled.

- A two-week multiple dose study (VIA-3196-02, NCT01519531) was conducted at doses of 5, 20, 50, 80, 100, and 200 mg per day in healthy subjects with mildly elevated low density lipoprotein (LDL) cholesterol (> 110 mg/dL).

- MGL-3196 was well tolerated at all doses with no dose-related adverse events or liver enzyme, ECG or vital-sign changes, except for a trend in diastolic BP reduction at the highest doses. There were no changes in standard laboratory safety tests including liver enzymes.
- Doses ranging from 50–200 mg demonstrated highly statistically significant reductions relative to placebo of up to: 30% for LDL cholesterol (range, $p = .05$ -.0001); 28% for non- high density lipoprotein (HDL) cholesterol (range, $p = .027$ -.0001); 24% for Apolipoprotein B (range, $p = .008$ -.0004), and statistical trends of up to 60% reduction in triglycerides (TG) (range, $p = .13$ -.016). The near maximal lipid effects were observed at a dose of 80 mg daily.
- Lipid lowering effects were confirmed in two Phase 1 clinical drug interaction studies in which either 100 or 200 mg of MGL-3196 was dosed in healthy volunteers for 9-11 days and on one or more day received a single dose of 20 mg simvastatin, 10 mg rosuvastatin or 20 mg atorvastatin. In these studies, the lipid lowering effects were even more pronounced than in the MAD, including a very significant reduction of 45% in TGs in subjects with elevated TGs, Lp(a) lowering of up to 40% in patients with measurable Lp(a), and up to 42% LDL-C lowering, the LDL-C result suggesting the potential for complementarity with statins.
- Overall, in the Phase 1 studies, there were no TEAEs including dose-related AEs consistently associated with MGL-3196 dosing and no laboratory abnormalities including liver enzyme abnormalities.
- In the multiple ascending dose study, subjects receiving the highest dose (200mg) experienced small reversible reductions in prohormone T4 levels, without an effect on active hormone T3, or TSH, that is considered most likely due to increased hepatic T4 deiodination and conversion to the active hormone T3. Importantly, no evidence of central thyroid axis suppression was observed in the MAD. The Phase 1 safety profile for MGL-3196 clearly differentiates it from previous thyroid analogues tested in Phase 1 studies,¹⁵ and confirms its selective pharmacologic action at the liver THR- β receptor.

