aspartate aminotransferase] levels, and one subject, who had elevated ALT before dosing with KB2115 developed a transient increase in ALT of 3-fold the upper level for normal.”²⁰ In a Phase 3 study of eprotirome in HeFH patients, statistically significant increases in AST, ALT, bilirubin and GGT were observed that were evident at week 2 and increased at week 6. The ALT elevations were on average 144-183% and AST 60-114 % increased over baseline. A comparative table showing the two week change in ALT and AST for MGL-3196 from the MAD study and eprotirome in the Phase 3 study is shown (Table 1). Approximately 50% of HeFH patients demonstrate > 1XULN elevation of ALT/AST after two weeks of dosing with eprotirome, whilst none of the subjects treated with clinically relevant doses of MGL-3196 showed AST or ALT elevations in 2 weeks. The results of the comparison must be viewed cautiously because the subjects treated with MGL-3196 as compared with eprotirome are different, HeFH patients typically taking several concomitant medications. In recent data submitted for publication (personal communication, [name]) the effect of thyroid hormone on liver enzymes (ALT, AST, bilirubin) in normal volunteers given at roughly 5X the replacement thyroxine dose was investigated. The study demonstrated no evidence of ALT/AST elevations in any subjects treated with high clinical doses of thyroxine for 2 weeks. The authors suggest that liver enzyme effects of eprotirome may be off-target, compound-specific or secondary to drug interactions rather than due to thyroid hormone receptor agonism.

Table 1 ALT, AST After Two Weeks of Clinical Dosing; MGL-3196, eprotirome

	Level	ALT		AST	
		Baseline	2 weeks	Baseline	2 weeks
Placebo	NL	12 (100*)	12 (100)	12 (100)	12 (100)
	>ULN	0 (0)	0 (0)	0 (0)	0 (0)
MGL-3196	5mg	NL	6 (100)	6 (100)	6 (100)
		>ULN	0 (0)	0 (0)	0 (0)
	20mg	NL	6 (100)	5 (83)	6 (100)
		>ULN	0 (0)	1 (17)	0 (0)
	50mg	NL	4 (66.6)	5 (83)	6 (100)
		>ULN	2 (33.3)	1 (17)	0 (0)
	80mg	NL	5 (83)	6 (100)	6 (100)
		>ULN	1 (17)	0 (0)	1 (17)
	100mg	NL	6 (100)	6 (100)	6 (100)
		>ULN	0 (0)	0 (0)	0 (0)
	200mg	NL	6 (100)	6 (100)	6 (100)
		>ULN	0 (0)	0 (0)	0 (0)

* percentage

Table 1 ALT, AST After Two Weeks of Clinical Dosing; MGL-3196, eprotirome
(Continued)

Level	ALT			AST		
	Baseline	2 weeks	6 weeks	Baseline	2 weeks	6 weeks
Placebo	NL	20 (87*)	23 (100)	21 (91)	20 (87*)	23 (100)
	ULN-2ULN	3 (13)		2 (9)	3 (13)	4 (17)
Eprotirome	50 µg	NL	18 (75)	7 (29)	5 (21)	21 (88)

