9.13 Drug Induced Liver Injury Monitoring

With any of the following liver function test elevations, patients should undergo repeat laboratory measurements as soon as possible, preferably within 72 hours (unless otherwise specified), and no later than 1 week. Local laboratory measurements may be used to facilitate follow-up:

- ALT or AST $>8 \times$ ULN;
- ALT or AST $>3 \times$ ULN and bilirubin $>2 \times$ ULN or International Normalized Ratio $>1.5 \times$ ULN;
- ALT or AST $>3 \times$ ULN with the appearance of fatigue, nausea, vomiting, right upper quadrant pain or tenderness, fever rash, and/or eosinophilia ($>5\%$); and
- ALT or AST $>5 \times$ ULN, regardless of symptoms should be followed up within 1 week.

Repeat evaluation should include AST, ALT, prothrombin time/International Normalized Ratio, total bilirubin, alkaline phosphatase, gamma-glutamyltransferase, creatinine, CK, and complete viral hepatitis screen. The patient should be questioned regarding symptoms, as well as potential causative factors. This information, including results and normal ranges of any laboratory parameters collected at a local laboratory, should be collected on the appropriate eCRF. Hepatobiliary ultrasonography and/or consultation with a hepatologist should be considered if clinically indicated.

Abnormal laboratory parameters should be followed at least weekly (more frequently as clinically indicated) until they have returned to baseline or have stabilized.

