3.8.2 Clinical Laboratory Assessments

3.8.2.1 Chemistry and Hematology

Descriptive statistics of each chemistry and hematology parameter will be presented for baseline values and for values and changes from baseline at each post-baseline visit. These will be presented by treatment group for each parameter using the Safety Population.

Counts and percentages of patients with any post-baseline observation that is below the lower limit of normal (<LLN) or above the upper limit of normal (>ULN) will be summarized for each chemistry and hematology parameter by treatment group and overall.

The liver enzyme parameters (ALT, AST, creatine kinase [CK], and GGT) will be analyzed for the overall Safety Population by active and placebo groups, and by exposure group, final dose group, and SHBG group. Statin subgroup will also be explored. Patients with mild liver diseases will not be included in the analysis of liver enzyme parameters, since the liver enzyme value will be affected. The possible liver disease may include, but is not limited to: elevated

liver enzymes (elevated direct bilirubin ≥ 0.3 mg/dL, or GGT > 100 U/L) or large amount of alcohol use.

The shift from baseline value to the worst post-baseline value will be summarized for selected parameters (AST, ALT, total bilirubin, alkaline phosphatase, creatinine, and CK). Shift categories will be based on normal ranges (<LLN, Normal, >ULN).

3.8.3 12-Lead Electrocardiogram

ECG parameters (heart rate, PR interval, QRS interval, QT interval, QTcB interval, QTcF interval, RR Interval, and overall interpretation) will be summarized by treatment group using descriptive statistics for the Safety Population. The average of 3 readings will be used in the summaries. For the overall interpretation, the most severe interpretation at the visit will be summarized. The count and percentage of patients with QTcF and/or QTcB above thresholds (>450 msec, >480 msec, >500 msec) or change from baseline above thresholds (>30 msec, >60 msec) will be summarized by treatment group for the Safety Population.

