3.8.6 Other Safety Parameters

Other safety data will be listed.

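### The SAP's liver analysis by exposure, final dose and SHBG group leaves out ALP and bilirubin, and the SAP names no summary for ALP isoenzymes

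*Protocol*

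**What the plan says.** Protocol 1.1.1 explains why the highest generally well-tolerated dose was not the no-adverse-effect level in each species. In the rat it was suppression of the thyroid axis; for the other species the text reads "in dog, generally monitorable biliary hyperplasia which was associated with elevated ALP". Protocol 1.1.2 says of an earlier thyroid agonist, in a Phase 3 study in HeFH patients, that "statistically significant increases in AST, ALT, bilirubin and GGT were observed". Protocol 10.2.3 gives ALT, AST and bilirubin as the markers of the liver-related events that the DSMB reviews.

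The SAP's dedicated liver analysis is in Section 3.8.2.1: "The liver enzyme parameters (ALT, AST, creatine kinase [CK], and GGT) will be analyzed for the overall Safety Population by active and placebo groups". The SAP then splits the same four parameters three further ways: on exposure, on final dose and on SHBG group. Statin subgroup is to be explored as well. The same section gives three other laboratory outputs: descriptive statistics for every chemistry parameter by treatment group; counts below LLN or above ULN for every chemistry parameter, by treatment group and overall; and a baseline-to-worst shift summary for AST, ALT, total bilirubin, ALP, creatinine and CK.

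Under Protocol 9.8, ALP and total and direct bilirubin are in the chemistry panel at every visit. ALP isoenzymes are measured at Baseline, Week 12 and Week 16. SAP 3.8.6 deals with the remaining data in one line: "Other safety data will be listed".

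**The concern.** The active arm is not one homogeneous dose group. Under Protocol 5.1 the Week 2 drug level decides whether a patient takes 100 mg or 60 mg from Week 4, and Protocol 1.2.2 expects about 25-30% of patients to exceed the target exposure at 100 mg. The SAP therefore splits its liver analysis by exposure and final dose. That split is where a level-related laboratory change would be looked for, and it omits the marker that the protocol ties to the dog finding. It also omits bilirubin, which the protocol treats as a liver marker in two places, and it includes CK, which is a muscle marker.

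At stake is what the trial can say about liver safety. A programmer who follows the SAP as written would produce no table showing whether ALP or bilirubin varies with exposure or final dose, although the data are collected at every visit. If ALP did move, no planned summary of the isoenzymes would help tell a liver source from a bone source.

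**Working it through.** The plan states no figure to reproduce, and the point rests on which parameters each analysis lists. Setting the outputs of SAP 3.8.2.1 side by side gives:

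| Parameter | Descriptive statistics by arm | LLN/ULN counts by arm and overall | Baseline-to-worst shift | By exposure, final dose and SHBG group |
|---|---|---|---|---|
| ALT | yes | yes | yes | yes |
| AST | yes | yes | yes | yes |
| GGT | yes | yes | no | yes |
| ALP | yes | yes | yes | **no** |
| Total bilirubin | yes | yes | yes | **no** |
| Direct bilirubin | yes | yes | no | **no** |
| CK (muscle) | yes | yes | yes | yes |

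1. *Count.* Six of the seven rows are liver-related (all except CK). Three of the six have the breakdown and 6 - 3 = 3 do not.
2. *Against the protocol's own lists.* Of the four markers reported for the earlier drug (AST, ALT, bilirubin, GGT), three are in the breakdown and bilirubin is not. Of the three DSMB markers (ALT, AST, bilirubin), two are in it and bilirubin is not. The one marker named for the dog finding, ALP, is not in it.
3. *Could a general rule bring them in?* No. SAP 3.1 bases safety summaries on MGL-3196 against placebo, and extends the exposure-level analysis only to the primary efficacy endpoint and selected secondary endpoints. The shift summary states no exposure or dose split, so the default two-group layout applies.
4. *ALP isoenzymes.* Protocol Appendix B puts them under additional parameters, outside the standard chemistry panel, so the chemistry summaries in SAP 3.8.2.1 do not clearly reach them. SAP 2.2 records that they are collected. No analysis section names them, which leaves the listing in SAP 3.8.6.
5. *What GGT covers.* GGT can reflect biliary effects and is in the breakdown, so coverage by exposure is reduced and not absent. One qualification applies. SAP 3.8.2.1 removes patients with mild liver disease from this analysis, with direct bilirubin of 0.3 mg/dL or more, or GGT above 100 U/L, among its examples. It does not say whether only baseline values count.

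**The case against.** The best answer is that the omission matters little. ALP and total bilirubin are tabulated by arm, and the ULN counts and shift summary work at patient level, so a subset of patients crossing ULN would show in both. GGT is in the breakdown, and the list holds three of the four markers raised by the earlier drug. Protocol 1.1.1 puts the clinical doses it considers (80-120 mg) "29-49 fold below the maximum dose that was generally well tolerated", and its dog no-adverse-effect margins are 13-fold at 80 mg and 6-fold at 120 mg. Protocol 1.1.1 and 1.1.2 report no liver-enzyme or mean liver-function changes of note in Phase 1, at up to 200 mg. All of this stands, and it limits the weight of the point. It does not supply the missing split: none of the by-arm tables shows exposure or final dose, a shift table based on the normal range misses rises within that range, and Phase 1 dosing lasted at most 14 days against 12 weeks here.

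Three stronger readings are tempting, and the documents do not support them.

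- *That the sponsor's data predict a cholestatic effect in patients.* The stated margins and the Phase 1 results do not support that, and Protocol 1.1.1 does not call the dog finding cholestatic.
- *That the loss can be expressed as power, by assuming an ALP rise confined to the 25-30% of patients above target exposure.* That subgroup is not the SAP's high-exposure group. Leaving aside the unit printed in SAP 3.1, its AUC cut-off of 5000 lies inside the protocol's 4000-9000 target range, so the group also takes in on-target patients, and its size is not stated. All active patients also go to 60 mg at Week 2, and those with high levels stay there, so a sustained effect of 100 mg in them is not what the design produces. The documents give neither an effect size nor an SD for ALP, and SAP 3.8.2.1 states no significance test.
- *That an ALP rise would go without follow-up because the retest criteria in Protocol 9.13 start from ALT or AST.* Protocol 9.8 has investigators notified of out-of-range values and requires appropriate follow-up. Section 9.1 has clinically significant values reported as adverse events and followed. The 9.13 repeat panel includes ALP, and one of its criteria uses bilirubin.

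**Conclusion.** The point holds as a gap in one SAP list. Three of six liver-related chemistry parameters, including the one that the protocol links to biliary hyperplasia in the dog, have no analysis by exposure, final dose or SHBG group, and ALP isoenzymes have no named summary. It does not invalidate the safety analysis: ALP and bilirubin are tabulated by arm, and GGT gives partial biliary coverage by exposure. A reader might take the presence of CK as a sign that it replaced ALP, but the SAP describes no substitution; CK is simply listed under a liver heading.

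The conclusion rests on reading the parameter list as closed and SAP 3.1 as the default for safety tables. It assumes no ALP effect of any size. The table shells are said to be in separate documents that were not available. If those shells already split ALP and bilirubin this way, the SAP text should say so.

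**What to change.** In SAP 3.8.2.1, change the liver list to ALT, AST, ALP, GGT, total bilirubin and direct bilirubin. Report CK separately as a muscle marker. Give all of them by arm, exposure group, final dose group and SHBG group. Add a descriptive summary of ALP isoenzymes at Weeks 12 and 16, by arm and by the same groups. Because direct bilirubin would then be both an analysed parameter and an example in the mild-liver-disease exclusion, state in the same edit at which time point that exclusion is judged.

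The cost is three added parameters by three groupings, 3 x 3 = 9 further breakdowns, plus the isoenzyme tables. All of them use data already collected, with no new sampling. The downside is more descriptive comparisons to read, so isolated differences should be interpreted with care.

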1.1.2 Comparative Liver Enzyme Effects

In the MGL-3196 SAD and MAD studies, the clinical laboratory values were considered unremarkable and none of the values outside of the reference range with the exception of lipid markers and T4 levels that were considered attributable to the pharmacology. There were no mean changes of note in hematology, chemistry, including liver and renal function, or in urinalysis. There were no effects on vital signs.

Because other thyroid agonists (eprotirome, Metabasis, MB-7811/ Viking, VK-2809) have reported liver enzyme abnormalities in Phase 1, 2, and 3 studies, a comparative analysis was made of MGL-3196 to other analogues, particularly to results from a recent report of eprotirome's Phase 3 study in HeFH patients.^{14,18,20,21} In Phase 1 studies, MB-7811 (now VK-2809) reported ALT and AST elevations peaking at about 1.5x ULN on day 14 of the study²² KB-2115 (eprotirome) in 14 day Phase 1 described: "the most frequent drug-related adverse events observed were mild increases in transaminase [alanine aminotransferase (ALT) and

aspartate aminotransferase] levels, and one subject, who had elevated ALT before dosing with KB2115 developed a transient increase in ALT of 3-fold the upper level for normal.”²⁰ In a Phase 3 study of eprotirome in HeFH patients, statistically significant increases in AST, ALT, bilirubin and GGT were observed that were evident at week 2 and increased at week 6. The ALT elevations were on average 144-183% and AST 60-114 % increased over baseline. A comparative table showing the two week change in ALT and AST for MGL-3196 from the MAD study and eprotirome in the Phase 3 study is shown (Table 1). Approximately 50% of HeFH patients demonstrate > 1XULN elevation of ALT/AST after two weeks of dosing with eprotirome, whilst none of the subjects treated with clinically relevant doses of MGL-3196 showed AST or ALT elevations in 2 weeks. The results of the comparison must be viewed cautiously because the subjects treated with MGL-3196 as compared with eprotirome are different, HeFH patients typically taking several concomitant medications. In recent data submitted for publication (personal communication, [name]) the effect of thyroid hormone on liver enzymes (ALT, AST, bilirubin) in normal volunteers given at roughly 5X the replacement thyroxine dose was investigated. The study demonstrated no evidence of ALT/AST elevations in any subjects treated with high clinical doses of thyroxine for 2 weeks. The authors suggest that liver enzyme effects of eprotirome may be off-target, compound-specific or secondary to drug interactions rather than due to thyroid hormone receptor agonism.

Table 1 ALT, AST After Two Weeks of Clinical Dosing; MGL-3196, eprotirome

	Level	ALT		AST	
		Baseline	2 weeks	Baseline	2 weeks
Placebo	NL	12 (100*)	12 (100)	12 (100)	12 (100)
	>ULN	0 (0)	0 (0)	0 (0)	0 (0)
MGL-3196	5mg	NL	6 (100)	6 (100)	6 (100)
		>ULN	0 (0)	0 (0)	0 (0)
	20mg	NL	6 (100)	5 (83)	6 (100)
		>ULN	0 (0)	1 (17)	0 (0)
	50mg	NL	4 (66.6)	5 (83)	6 (100)
		>ULN	2 (33.3)	1 (17)	0 (0)
	80mg	NL	5 (83)	6 (100)	6 (100)
		>ULN	1 (17)	0 (0)	1 (17)
	100mg	NL	6 (100)	6 (100)	6 (100)
		>ULN	0 (0)	0 (0)	0 (0)
	200mg	NL	6 (100)	6 (100)	6 (100)
		>ULN	0 (0)	0 (0)	0 (0)

* percentage

Table 1 ALT, AST After Two Weeks of Clinical Dosing; MGL-3196, eprotirome
(Continued)

Level	ALT			AST		
	Baseline	2 weeks	6 weeks	Baseline	2 weeks	6 weeks
Placebo	NL	20 (87*)	23 (100)	21 (91)	20 (87*)	23 (100)
	ULN-2ULN	3 (13)		2 (9)	3 (13)	4 (17)
Eprotirome	50 µg	NL	18 (75)	7 (29)	5 (21)	21 (88)
		ULN-2ULN	6 (25)	10 (42)	14 (58)	3 (13)
		2ULN-3ULN		5 (21)	3 (13)	4 (17)
		3ULN-4ULN		2 (8)	2 (8)	
Eprotirome	100 µg	NL	20 (91)	9 (41)	4 (18)	20 (91)
		ULN-2ULN	2 (9)	7 (32)	11 (50)	2 (9)
		2ULN-3ULN		4 (18)	3 (14)	3 (14)
		3ULN-4ULN		2 (9)	3 (14)	
		4ULN-5ULN			1 (5)	

*percentage

1.2 Rationale for Phase 2 HeFH Study Design

Doses of 80-200 mg per day of MGL-3196 appeared to have similar effects on lipids after 14 days of dosing in a modest number of otherwise-healthy volunteers with mildly elevated LDL-C; effects in patients with HeFH or in individuals dosed for longer periods may differ. Results of the completed clinical studies, including robust lipid changes observed in the MAD and MGL-3196-03, suggest that MGL-3196 is suitable for once-daily dosing, and that it can be dosed with or without food. Based on the dose-related lipid effects, the doses of MGL-3196 planned for the Phase 2 study in HeFH patients is 100 mg/day (range of projected mean exposure ~4000–9000 ng*hr/ml), to be given once-daily without regard to food.

Patients with HeFH typically take high dose statins, particularly atorvastatin and rosuvastatin with ezetimibe^{21,23} to achieve therapeutic targets. MGL-3196's mechanism of cholesterol lowering is complementary to statins.⁵ MGL-3196 provides additional benefits, potently lowering triglycerides and, like other thyroid agonists appears to reduce Lp(a), a particularly atherogenic particle frequently elevated in HeFH, including severe HeFH.

